7.6 Follow up laboratory procedures

7.6.1 7 day Post End of Treatment

Drug Safety Assessment - all subjects (+/-7 days)

To be completed on all subjects one week after the last study dose of valganciclovir.

- Anticipated to be study day 107 in prophylaxis group
- To be scheduled one week post last study dose of valganciclovir in preemptive group (which may be beyond day 107)

All subjects will have the following laboratory assessments completed at the transplant center while hospitalized. If discharged, laboratory assessments may be collected at routine care follow-up clinic appointments, at skilled nursing facilities, rehabilitation facilities, or outpatient laboratories.

The following laboratory assessments are anticipated to have been obtained as standard of care and will only be drawn specifically for the study if not completed as standard care within the allowable specified window of +/-7 days.

- Hematology
 - Hemoglobin
 - Hematocrit %
 - Platelets
 - WBC with differential for absolute neutrophil calculation
- Chemistry
 - Blood urea nitrogen
 - Creatinine
 - Total bilirubin
 - AST
 - ALT

7.6.2 Immunologic studies (immune assays and lymphocyte count) All subjects

98 days, 6 month and 12month (+/- 14 days)

Subjects will have study specific serum samples obtained for Immune Assay testing and a lymphocyte count [proportion of white blood cells (hematology) that are lymphocytes] at study day 98, and at 6 months and 12 month (post-transplant) time point. Each sample may be obtained within +/- 14 day window. This blood sample may be obtained at the transplant center if hospitalized. If discharged, blood may be collected during routine follow-up clinic appointments, at outpatient laboratories, skilled nursing facilities, or rehabilitation facilities. Lymphocyte counts may be done as standard care at the local lab and recorded for the study purpose. If not completed as standard care, the site investigator will order the lymphocyte count to be drawn and processed locally and the results will be recorded.

Immune assays will be done by the [name] Lab at Fred Hutchinson Cancer Research Facility in Seattle Washington. Results of immune assays will be provided only to the coordinating center since these results do not impact subject care. All materials, shipping supplies, and instructions for immune assays will be provided to the remote location. Please see laboratory manual for all process and storage directions.

7.6.3 Pregnancy test for all females of childbearing potential

End of Treatment (+3 month)

All female subjects of childbearing potential will have a onetime post treatment pregnancy test. The pregnancy test may be performed on urine or blood and will be performed after the end of treatment up to 3 month post end of treatment.

All female subjects of childbearing potential will have a pregnancy test completed at the transplant center while hospitalized. If discharged, pregnancy test may be collected at routine care follow-up clinic appointments, at skilled nursing facilities, rehabilitation facilities, or outpatient laboratories.

7.6.4 Suspected CMV disease sample collection (Study day 1 – 12 month)

Subjects in either group suspected to have CMV disease based on the assessment of the clinician or the investigator will have a blood sample sent to the central lab for CMV DNA PCR testing. This sample collection may occur at any time point throughout the 12 month

duration of the study. In preemptive therapy group, this sample will be in addition to the weekly CMV testing sample. This blood sample will be obtained at the transplant center if hospitalized. If discharged, blood may be collected during routine follow-up clinic appointments, at outpatient laboratories, skilled nursing facilities, or rehabilitation facilities. Resistance testing will be completed at the University of Washington virology laboratory. All materials, shipping supplies, and instructions will be provided to the remote location. Please see laboratory manual for all process and storage directions. These results will be reported to the site via fax.

7.6.5 CMV resistance testing

Study day 1 – 12 month

(This one time study visit may occur at any time point throughout the 12 month duration of the study)

For those subjects who demonstrate no reduction in viral load after three weeks of ganciclovir/valganciclovir employed for CMV viremia in the preemptive therapy group or for the treatment of CMV disease in subjects in either study group, assessment of genotypic resistance for UL97 and UL54 mutations may be undertaken. This blood sample will be obtained at the transplant center if hospitalized. If discharged, blood may be collected during routine follow-up clinic appointments, at outpatient laboratories, skilled nursing facilities, or rehabilitation facilities. Resistance testing will be completed at the University of Washington virology laboratory. All materials, shipping supplies, and instructions will be provided to the remote location. Please see laboratory manual for all process and storage directions.

7.7 Non-laboratory Procedures and Clinical Assessments Schedule (see also Schedule of Procedures appendix A)

7.7.1 Study day 1-100

Drug administration phase

Prophylaxis therapy group will begin to receive antiviral prophylaxis treatment on day 1 and will continue receiving a daily dose through day 100. Please see protocol section 6.2 for a complete description and instructions regarding of prophylaxis dosing.

Preemptive treatment group will begin preemptive antiviral drug therapy during study days 1-100 only when viremia is detected by weekly surveillance and will continue preemptive therapy until two consecutive weekly CMV PCRs are negative. Therapy may be repeated if further detection of viremia is detected during the 100 day period.

7.7.2 Study day 1-107

(Drug treatment safety labs phase)
Monitoring and managing neutropenia

Neutropenia is the most commonly encountered toxicity of ganciclovir formulations (IV ganciclovir and valganciclovir). Guidance for the evaluation and management of neutropenia are provided in the study manual of operations. If necessary, administration of valganciclovir may be interrupted temporarily and subsequently re-started in response to neutropenia. If the drug has to be interrupted for more than 14 consecutive days for a given interruption episode, the site investigator may contact the study PIs to determine if there are circumstances in which it may be appropriate to re-start the drug. Otherwise, valganciclovir should be discontinued permanently and subjects should be followed as discussed in the section on handling of discontinuations.

7.7.3 Study day 1 through one year

Outcome data recording

After randomization and throughout the entire study period, all subjects will be followed and data collected related to study outcomes. All evaluations monitored will be completed as standard of care and not specifically for the study. Data collection and follow-up will be primarily achieved by medical record review at each study visit time point. Record reviews will include transplant hospital, out-patient clinics, outside hospitals, skilled nursing centers, and rehabilitation hospital records. Non-study hospital physicians and/or subjects may be contacted to verify whether or not they have had any additional hospitalizations or clinic visits outside of the transplant hospital in order to confirm complete collection of all outcome data.

Specific outcome data to be followed and recorded include:

- Evaluations for suspected and confirmed CMV disease
- All treatments for suspected and confirmed CMV disease
- Evaluations for organ rejection
- All treatments for organ rejection
- Graft loss and need for liver retransplantation
- Fungal, major bacterial, and non-CMV viral infections
- All-cause mortality during the 12 month
- All immunosuppressant taken during 100 days
- Immunosuppressant given for the treatment of rejection episodes for the 12 month period
- Immunosuppressant medication levels taken as standard of care
- Hospitalization status

7.7.4 Adverse Event Monitoring and Reporting (Study day 1 through 7 days post end of study treatment phase)

All subjects will be assessed for adverse events throughout the administration of drug period plus 7 days. This is anticipated to be study day 1 through 107 for prophylaxis group subjects. Preemptive therapy arm monitoring of AEs timelines will be individually determined based on the length of treatment for viremia detected during study days 1-100. Please see adverse event section for complete description of adverse event monitoring and reporting.

7.7.5 Study Specific Medication Compliance Visit (Study day 30, 60, and end of treatment +14 days)

The Clinical Research Coordinator will track valganciclovir administration while the subject is in the hospital using hospital medication administration records. If the subject is discharged to a skilled nursing facility or rehabilitation facility, medication administration records will also be used to track valganciclovir administration. Upon discharge, if at home, the subject will be contacted and interviewed at day 30, 60 and end of treatment to assess drug compliance. These interviews may occur up to 14 days after the specified visit day.

A source document designed and provided by the coordinating center will be required to verify data acquired by interview with subjects regarding compliance with valganciclovir drug regimen. This interview may be conducted in person or by telephone. Using a non-judgmental approach, medication compliance will be assessed by interviewing subjects. Subjects will be requested to recall the number of missed doses in the previous reporting period. The coordinator will calculate percentage of compliance based on the subject's self- report. The compliance interview source document can be found on the CAPSIL website.

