The participating sites are currently using valganciclovir prophylaxis for 100 days after liver transplantation for CMV prevention as standard of care with drug costs charged to the patient or third-party payers as part of routine clinical care. In this study, one group of subjects will continue to receive standard of care (valganciclovir prophylaxis) and the other group will receive preemptive therapy with valganciclovir only upon evidence of CMV infection. For the group randomized to preemptive therapy, the drug use is estimated to be 43% less. No additional costs for valganciclovir use for study purposes will be incurred by the participating institution, subject or another party for participants randomized to either preemptive therapy or to prophylaxis.

Use of model for end-stage liver disease (MELD) scoring system as the basis for prioritizing organ allocation by the United Network for Organ Sharing in the current era has led to a substantially higher number of patients undergoing transplantation who have renal dysfunction or are requiring dialysis than time in the previous years (53,54). In order that our study is considered representative of liver transplantation practices at present and in order for our findings to be generalized to the transplant population undergoing in current clinical settings, it is important to include liver transplant subjects that require dialysis. Data in patients on dialysis have documented no pertinent issues that could influence the pharmacokinetics and bioavailability of valganciclovir in the study subjects (55). Furthermore, all study sites are currently using valganciclovir in dialyzed patients as standard of care. Receipt of dialysis has no effect on CMV disease rate in transplant recipients. However, given higher post-transplant mortality in patients receiving dialysis (56), subjects will be stratified by receipt of dialysis and sample size calculations will take into consideration the mortality within the first year.

We propose to conduct a randomized trial comparing prophylaxis versus preemptive therapy for the prevention of CMV disease in R-/D+ liver transplant recipients. The key goals of the study are to assess the efficacy of the 2 clinically used approaches for CMV prevention and not the efficacy of the drug per se. In this regard, this is a strategy trial based on the clinical practice of medicine using a drug that is currently the standard of care in these patients.

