2.3.1.2.6 Summary of human toxicity data

Ganciclovir-related neutropenia occurs very uncommonly in persons without underlying bone marrow dysfunction and generally occurs at a median of 5 weeks after drug exposure. In patients without underlying bone marrow dysfunction, two recent trials showed very low rates of neutropenia after 3-4 weeks of ganciclovir at doses similar to those proposed in this protocol (2% within first 4 weeks with prophylaxis of 900 mg VGCV/day (9); 1.2% at day 21 with 900 mg valganciclovir twice daily; 0% at day 21 with 5 mg/kg ganciclovir twice daily (57). There is no convincing evidence that ganciclovir or valganciclovir cause thrombocytopenia.

Anemia has been observed in HIV-infected subjects, but there is no evidence that it is a problem in transplant patients or in the treatment of congenital disease. There may be some risk of renal toxicity, however, this was not consistently observed across randomized trials. Other potential safety issues include teratogenicity and carcinogenicity.

Summary of ganciclovir and valganciclovir toxicities		
Adverse effect	Human data	Documented in randomized trials
Neutropenia	Yes	Yes
Thrombocytopenia	Yes	No
Anemia	Yes	Some (HIV only)
Renal dysfunction	Yes	No (none in recent trials)
Gastrointestinal effects	Yes	Yes
Tumors	No	No
Birth Defects	No	No

Data in Table summarized from references 9, 55-63

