9.2.3 CAPSIL Definition

For the CAPSIL study, a reportable adverse event is defined as:

1. Any clinically important untoward medical occurrence in a subject receiving study drug that is different from what is expected in the clinical course of a patient with a liver transplant (see appendix C for events considered to be part of the expected course of liver transplant).

OR

2. Any clinically important, untoward medical occurrence that is thought to be related to the study drug, regardless of the “expectedness” of the event for the course of a patient with a liver transplant. Expected events for liver transplant are untoward clinical occurrences that are deemed by the investigator to occur with reasonable frequency in the day-to-day care of patients with a liver transplant (see appendix C for events considered to be part of the expected course of liver transplant).

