9.8.3 Halting rules

1. All-cause mortality compared at interim analysis will be used as safety parameter for halting the trial. With 60 subjects enrolled, a difference in survival probability of greater than 37% would be detected at the .05 level with 90% power. Thus an important difference in mortality between the two groups if documented will be detected at interim analysis and DSMB recommended action can be undertaken. The table below depicts minimal detectable hazard ratio with sample size of 60.

Safety endpoint			
At interim-Minimal detectable hazard ratio with sample size of 60 at alpha=.05, power=.9:			
Probability of survival (inferior regimen)	Probability of survival (superior regimen)	Events	Hazard ratio
.600	.976	13	.048
.550	.950	16	.089

2. Halting for a difference in reportable SAEs will be done upon the recommendation of the DSMB if there is a statistically significant difference in reportable SAEs at the .05 level after at least 20 subjects are enrolled.

3. A statistically significant difference ($p=0.001$) of more than 50% between the two groups in the incidence of CMV disease after 1 year follow of 60 subjects.

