12.6.3 Adverse events

Severe, unexpected drug related adverse events will be compiled and compared between the two groups. Adverse events will be evaluated by comparing the total number of reportable adverse events per person day of follow up between the two regimens. The analysis

will be repeated stratified by receipt of anti-lymphocyte induction and renal dialysis using Mantel-Haenzel weights. The analysis will include assessment of baseline comparability of the comparison groups and if necessary, will adjust for items not adequately controlled by randomization in additional models.

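### Reportable AE/SAE collection follows drug exposure in the preemptive arm, and neither the AE rate nor SAE halting rule 2 is matched to the time in which an event could be reported

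*Combined protocol and SAP*

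**What the plan says.** **Window.** Section 7.7.4 states: "All subjects will be assessed for adverse events throughout the administration of drug period plus 7 days". For prophylaxis it adds: "This is anticipated to be study day 1 through 107 for prophylaxis group subjects". For the preemptive arm: "Preemptive therapy arm monitoring of AEs timelines will be individually determined based on the length of treatment for viremia detected during study days 1-100". Section 8.1.2 repeats this rule. Section 9.5 and Appendix A note 6 refer to the intervention period plus a week, and 9.5 also lets the preemptive end date vary with treatment for viremia.

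**Definition.** Limb 1 of the reportable-event definition in 9.2.3 is: "Any clinically important untoward medical occurrence in a subject receiving study drug", where the event is not part of the expected transplant course. Limb 2 covers events thought to be related to the drug.

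**Analysis.** Section 12.6.3 evaluates adverse events by "comparing the total number of reportable adverse events per person day of follow up between the two regimens". Follow-up is not defined there. The only evaluation period defined (12.4.5, for CMV disease) runs from randomization to last contact.

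**Halting.** Rule 2 in 9.8.3 provides for halting on the DSMB's recommendation "if there is a statistically significant difference in reportable SAEs at the .05 level after at least 20 subjects are enrolled". It names no test, denominator or window.

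**The concern.** The trial compares two strategies; section 2.2.2 says its aim is not the efficacy of the drug itself. An unexpected event in a preemptive subject who is being monitored but not treated therefore belongs to the preemptive strategy. Under the literal wording of 7.7.4 and limb 1 of 9.2.3 it may not be reportable, whereas the same event in a prophylaxis subject on daily drug is.

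Viremia, which arises after randomization, sets the length of the preemptive window, so randomization does not balance it. A subject who never becomes viremic has no stated window at all.

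If events are collected over unequal windows but divided by similar follow-up time, the arm with the shorter window shows a lower rate even when the true rates are equal. The SAE counts behind rule 2 come from the same windows. If sites read the conflicting passages differently, the window will also vary between sites.

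**Working it through.** **1. The plan's own figure.** 100 days of prophylaxis (6.2.2.1) + 7 = day 107, as stated.

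**2. The passages side by side.**
- Exposure-dependent: the text of 7.7.4, 8.1.2, and limb 1 of 9.2.3.
- Open to a common minimum of day 107: the 7.7.4 heading, which runs from study day 1 to a week after the treatment phase (headed as days 1 to 100 in 7.5); 9.5, with the intervention period given as 100 days in section 4; and Appendix A, which ticks AEs/SAEs in its all-subjects block.
- No text says which prevails.

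**3. Null rate ratio.** Let the true daily rate λ and the follow-up F per subject be equal in both arms, and let W be the reporting window. The expected rate is λW/F in each arm, so the ratio is W(preemptive)/W(prophylaxis).

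**4. Illustrative windows.** Section 2.2.2 says of the preemptive arm that "the drug use is estimated to be 43% less". It gives no unit. Taking the window as drug days plus 7:
- If 43% means days: 100 × 0.57 = 57; 57 + 7 = 64; 64/107 = 0.60.
- If it means quantity: 0.57 × 100 × 900 mg = 51,300 mg; at 1,800 mg per day (6.2.1, before renal adjustment) that is 28.5 days; 28.5 + 7 = 35.5; 35.5/107 = 0.33.

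**5. Other readings.**
- The window opens on day 1 and closes 7 days after the last dose. With an assumed 30 days before the first dose: (64 + 30)/107 = 0.88 and (35.5 + 30)/107 = 0.61.
- Day 107 is a minimum and treatment runs on. For an assumed last dose on day 121: 128/107 = 1.20.
- Follow-up in 12.6.3 means time under AE reporting: the window cancels and the ratio is 1.

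**6. Halting rule 2.** The documents give no SAE rate, so the values here are assumptions. For true SAE risk p over 107 days, equal in both arms, the recorded preemptive risk is q = 1 − (1 − p)^r, with r = 0.60 or 0.33 from step 4. For p = 15%, q = 9.3% or 5.2%; for p = 10%, q = 6.1% or 3.4%. The table gives the chance of p < .05 at one look, by two-sided Fisher's exact test on subjects with an SAE, when there is no true difference.

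| Subjects | Assumed SAE risk | Common window | r = 0.60 | r = 0.33 |
|---|---|---|---|---|
| 20 | 10% | 0.1% | 0.1% | 0.1% |
| 20 | 15% | 0.4% | 0.4% | 0.6% |
| 60 | 10% | 0.9% | 1.4% | 2.9% |
| 60 | 15% | 1.7% | 3.6% | 8.8% |
| 176 | 5% | 1.8% | 3.7% | 9.1% |
| 176 | 10% | 3.0% | 10% | 31% |
| 176 | 15% | 3.1% | 16% | 51% |

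Higher event rates change the picture. With an assumed 0.5 SAEs per subject per 107 days, an exact conditional Poisson test on counts gives 4.9% or 12.5% at 20 subjects, 17% or 55% at 60, and 48% or 96% at 160 (windows of 64 or 35.5 days).

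**The case against.** **Direction.** The heading of 7.7.4, section 9.5 and Appendix A support a window to at least day 107 in both arms, and 7.6.1 notes that the preemptive end-of-treatment check may fall later than day 107. Individual determination would then lengthen the preemptive window. This stands: a reader might infer a proven bias of 0.33 to 0.60 toward preemptive therapy, but the documents do not establish one. What remains is that the contrary text of 7.7.4, 8.1.2 and 9.2.3 is not reconciled with that reading.

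**Missed harms.** A reader might also infer that harm from delayed treatment goes uncaptured. It largely does not: 7.7.3 collects CMV disease, infections, rejection, graft loss and death in all subjects through one year, and 9.4.1.1 deliberately keeps these endpoints out of SAE reporting.

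**Late neutropenia.** Section 2.3.1.2.6 says that ganciclovir-related neutropenia "generally occurs at a median of 5 weeks after drug exposure", which may suggest that a short preemptive window closes too early to see it. But 7.5.3.1 draws safety labs in both arms whether or not drug is taken and reports low ANC as an adverse event, and 12.6.2.1 analyses protocol labs. Section 2.3.1.2.1.1 ties the 5-week figure to stem-cell recipients.

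**Halting rule.** It would be wrong to quote 16% to 51% as the rule's false-signal rate. Those figures need full enrolment and an assumed 15% SAE risk. Endpoints and the long Appendix C list are excluded from reportable SAEs, so low rates are plausible. Halting also needs a DSMB recommendation.

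**Even-handed rule.** Drug period plus 7 days is stated for all subjects, so a prophylaxis subject who stops early could also have a shorter window. Exposure-based collection suits drug-related events, which limb 2 covers in any case. The AE rate is not a listed outcome in 3.2. These points limit the stakes, but they do not justify an unmatched denominator for a comparison of strategies.

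**Conclusion.** The point holds as an unreconciled reporting window and an unmatched comparison. If sites follow 7.7.4 and limb 1 of 9.2.3 literally, reportable events in untreated preemptive time are under-counted and the 12.6.3 comparison leans toward that arm.

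The size is not fixed by the documents. The ratios 0.60 and 0.33 assume that 43% measures days or quantity, that the window equals drug days plus 7, and that both arms share the same follow-up denominator. Opening the window on day 1 brings the ratio nearer 1; treating day 107 as a minimum could take it above 1.

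For rule 2, at assumed SAE risks of 10% to 15%, the spurious-signal chance is 0.1% to 0.6% at 20 subjects and 1.4% to 8.8% at 60. It grows with enrolment and event rate.

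The primary endpoint, infections, rejection, graft loss, mortality and laboratory neutropenia are not affected. The correction should still be made, because the reportable AE/SAE comparison feeds a halting rule and the change is cheap.

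**What to change.** 1. Use one AE/SAE window for every randomized subject in both arms: study day 1 through the later of day 107 and 7 days after the last study dose, whether or not drug is being taken. This also covers never-treated preemptive subjects and prophylaxis subjects who stop early.
2. In limb 1 of 9.2.3, replace the restriction to subjects on study drug with *in a randomized subject during the reporting window*.
3. Align 7.7.4, 8.1.2, 9.5 and Appendix A note 6 with this window.
4. In 12.6.3, define the denominator as days within the reporting window. For the between-arm comparison, restrict both events and days to the common days 1 to 107. Report on-drug events and events after day 107 separately.
5. Base halting rule 2 on events within the same days 1 to 107, and name its test.

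With a common window and matching denominator the expected null rate ratio is 1.00, and the single-look false-signal chance for rule 2 is at most 4.1% across the scenarios calculated.

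The cost is protocol and SAP wording and somewhat more event reporting in the preemptive arm. Section 9.4 already requires investigators to review all subjects' records at each study visit, so no new visits are needed.
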